## 5.2. Serious Adverse Events

The term "Serious Adverse Event" (SAE) is defined in 21 CFR 312.32 as follows: "An adverse event or suspected adverse reaction is considered serious if, in the view of either the investigator or the sponsor, it results in any of the following outcomes: Death, a life-threatening adverse event, inpatient hospitalization or prolongation of existing hospitalization, a persistent or significant incapacity or substantial disruption of the ability to conduct normal life functions, or a congenital anomaly/birth defect. Important medical events that may not result in death, be life-threatening, or require hospitalization may be considered serious when, based upon appropriate medical judgment, they may jeopardize the patient or subject and may require medical or surgical intervention to prevent one of the outcomes listed in this definition. Examples of such medical events include allergic bronchospasm requiring intensive treatment in an emergency room or at home, blood dyscrasias or convulsions that do not result in inpatient hospitalization, or the development of drug dependency or drug abuse."

"Life threatening" refers to an AE or suspected adverse reaction that represents an immediate risk of death to the subject. It does not include an AE or suspected adverse reaction that, had it occurred in a more severe form, might have caused death. Similarly, a hospital admission for an elective procedure is not considered a SAE.

## 5.3. Adverse Event Reporting to the IND Sponsor

AEs that meet SAE criteria must be reported and submitted by the clinical site on an expedited basis to the IND Sponsor, VRC/NIAID/NIH, according to sponsor guidelines as follows:

- Results in death,
- Is life threatening (places the subject at immediate risk of death from the event as it occurred),
- Results in inpatient hospitalization or prolongation of existing hospitalization,
- Results in a persistent or significant disability/incapacity,
- Results in a congenital anomaly/birth defect in the offspring of a study subject, OR
- Based upon appropriate medical judgment, may jeopardize the subject's health and may require medical or surgical intervention to prevent one of the other outcomes listed in this definition (examples of such events include allergic bronchospasm requiring intensive treatment in the emergency room or at home, blood dyscrasias or convulsions that do not result in inpatient hospitalization, or the development of drug dependency or drug abuse).

In addition, any event, regardless of severity, which in the judgment of an investigator represents a SAE, may be reported on an expedited basis.

An investigator will communicate an initial SAE report within 24 hours of site awareness of occurrence to the IND Sponsor by data entry into the database, which triggers an alert to the IND Sponsor Medical Officer. Within 3 working days, a written summary by the investigator should be submitted to the IND Sponsor.

In order for the IND Sponsor to comply with regulations mandating sponsor notification of specified SAEs to the FDA within 7 and/or 15 calendar days, the investigator must submit additional information as soon as it is available.

## 5.4. **Reporting of Pregnancy**

Pregnancy is not an adverse event, but pregnancy, if it occurs during the time of study participation, will be recorded in the study database, and notification on the pregnancy will be distributed to the study team and to the IND Sponsor. Women will be followed for clinical safety and to collect the pregnancy outcome as described in Section 4.4.7. Congenital abnormalities or birth defects and spontaneous miscarriages that meet serious criteria (Section 5.2) will be reported as SAEs. Pregnancy outcome will be reported to the IND Sponsor and to regulatory agencies.

## 5.5. IND Sponsor Reporting to the FDA

The IND Sponsor is responsible for making the determination of which SAEs are "serious and unexpected suspected adverse reactions" (SUSARs) as defined in 21 CFR 312.32. The following definitions apply:

- *Suspected Adverse Reaction* means any AE for which there is a reasonable possibility that the drug caused the AE.
- Unexpected Adverse Event means an AE that is not listed (refer to Risks in Section 8.5) at the specificity or severity that has been observed.

All SUSARs (as determined by the IND Sponsor) will be reported to the FDA as IND Safety Reports per 21 CFR 312.32 as soon as possible but not exceeding 7 calendar days for unexpected fatal or life-threatening events, and not exceeding 15 calendar days for other qualifying events. IND Safety Reports will also be provided to the IRB.

The IND Sponsor will also submit an IND Annual Report of the progress of the investigation to the FDA as defined in 21 CFR 312.33.

## 5.6. Reporting to the Institutional Review Board

The following information is consistent with NIH IRB Policy 801: Reporting Research Events, Version 1, effective July 1, 2019.

*Reportable Event* - An event that occurs during the course of human subject research that requires notification to the IRB.

For the purposes of this policy, reportable events include the following:

- Unanticipated Problems (UPs) involving risks to subjects or others
- Non-compliance (including major protocol deviations and noncompliance that is not related to a protocol deviation)
- Deaths related or possibly related to research activities
- New information that might affect the willingness of subjects to enroll or continue participation in the study

#### 5.6.1. Unanticipated Problem

An Unanticipated Problem (UP) is defined as any incident, experience, or outcome that meets all the following criteria:

- Unexpected (in terms of nature, severity, or frequency) given (a) the research procedures that are described in the protocol-related documents, such as the IRB approved research protocol and informed consent document; and (b) the characteristics of the subject population being studied; and
- Related or possibly related to participation in the research (possibly related means there is a reasonable possibility that the incident, experience, or outcome may have been caused by the procedures involved in the research); and
- Suggests that the research places subjects, or others (which may include research staff, family members or other individuals not directly participating in the research) at a greater risk of harm (including physical, psychological, economic, or social harm) related to the research than was previously known or expected.

A UP must be reported within 7 calendar days of an investigator becoming aware of the actual or suspected UP.

#### 5.6.2. Non-Compliance

Non-compliance is the failure of investigator(s) to follow the applicable laws, regulations, or institutional policies governing the protection of human subjects in research, or the requirements or determinations of the IRB, whether intentional or not.

Non-compliance may be unintentional (e.g. due to lack of understanding, knowledge, or commitment), or intentional (e.g. due to deliberate choice to ignore or compromise the requirements of any applicable regulation, organizational policy, or determination of the IRB).

Non-compliance is further characterized as serious or continuing as follows:

- Serious non-compliance Non-compliance, whether intentional or not, that results in harm or otherwise materially compromises the rights, welfare and/or safety of the subject. Non-compliance that materially effects the scientific integrity or validity of the research may be considered serious non-compliance, even if it does not result in direct harm to research subjects.
- Continuing non-compliance A pattern of recurring non-compliance that either has resulted, or, if continued, may result in harm to subjects or otherwise materially compromise the rights, welfare and/or safety of subjects, affect the scientific integrity of the study or validity of the results. The pattern may comprise repetition of the same non-compliant action(s), or different noncompliant events.

Any actual or suspected non-compliance by any investigator or entity associated with the protocol must be reported to the IRB by the PI/designee within 7 calendar days of any investigator or individual associated with the protocol first becoming aware.

#### **5.6.3.** Protocol Deviation

A Protocol Deviation (PD) is defined as any change, divergence, or departure from the IRBapproved research protocol and are further characterized as major and minor as follows:

- Major Deviations Deviations from the IRB approved protocol that have, or may have the potential to, negatively impact, the rights, welfare or safety of the subject, or to substantially negatively impact the scientific integrity or validity of the study.
- Minor Deviations Deviations that do not have the potential to negatively impact the rights, safety, or welfare of subjects or others, or the scientific integrity or validity of the study.

For the reporting purposes, failure of subjects to comply with the research protocol does not represent non-compliance unless that failure is due to an action or omission of a member of the research team, for example, the failure to give adequate instruction to the subject.

A major deviation must be reported within 7 calendar days of an investigator becoming aware of an actual or suspected deviation. Although PDs are also non-compliance, these should only be reported once as deviations. Major deviations resulting in death must be reported within 24 hours of the occurrence of the event or of any member of the study team becoming aware of the death.

Researchers are responsible for monitoring their studies throughout the year for adherence to the IRB approved protocol. The purpose of this monitoring is to identify major deviations and to look for trends in minor deviations that may indicate a systemic issue in how the study is being conducted that could potentially negatively impact the rights, safety, or welfare of participants or the study's ability to produce scientifically valid results. A series of minor deviations pointing toward a more global issue that could affect the rights, safety or welfare of the participant or affect the validity of the study should be reported as a major deviation. In all other instances, a summary of minor deviations should be provided to the IRB at the time of continuing review.

#### 5.6.4. Death

Any death of a research subject that is possibly, probably or definitely related to the research must be reported within 24 hours of an investigator becoming aware of the death.

#### 5.6.5. New Information

New information that might affect the willingness of a subject to enroll or remain in the study should be reported within 7 calendar days of an investigator first becoming aware.

#### 5.6.6. Suspension or Termination of Research Activities

Any suspension or termination of research activities, including holds on new enrollment, placed upon the research by the study sponsor, NIH or IC leadership, or any regulatory agency must be reported within 7 calendar days of an investigator becoming aware.

#### 5.6.7. Expedited Reporting to the IRB

Death related to research must be reported within **24 hours**.

The following will be reported within 7 calendar days of investigator awareness:

- Actual or suspected UPs,
- Actual or suspected non-compliance,
- Actual or suspected Major PDs,
- SAEs that are actual or suspected UPs,
- New information that might affect the willingness of a subject to enroll or remain in the study,
- Suspension or termination of research activities, including holds on new enrollment, placed upon the research by the study sponsor, NIH or IC leadership, or any regulatory agency.

#### 5.6.8. Annual Reporting to the IRB

The following will be reported to the IRB in summary at the time of Continuing Review:

- Summary of UPs and non-compliance,
- AEs, including SAEs, that are not UPs, as a narrative summary statement indicating whether these events were within the expected range,
- Minor PDs (aggregate summary),
- Any trends or events which in the opinion of the investigator should be reported.

## 6. STATISTICAL CONSIDERATIONS

## 6.1. Overview

This is a Phase I, open-label, dose escalation study to evaluate the dose, safety, tolerability, and immunogenicity of the mosaic quadrivalent influenza vaccine VRC-FLUMOS0111-00-VP. Study objectives can be found in STUDY OBJECTIVES.

## 6.2. Sample Size and Accrual

In Part A, 35 healthy adult participants were enrolled in the study. In Group 1A-1B, five subjects were enrolled, and in Groups 2A-2B and 3A-3B, fifteen healthy adult participants subjects were enrolled in each group respectively.

In Part B, recruitment will target 26, and potentially 39 subjects if needed for additional safety and immunogenicity evaluation at the 60 mcg dose level (Group 6). In part C, recruitment will target 26 healthy adult participants, if needed, after analysis of Part A and B safety and immunogenicity data. Up to 110 participants may be enrolled if necessary for safety or immunogenicity evaluations.

## 6.3. Endpoints

#### 6.3.1. Primary Endpoints: Safety

Assessment of product safety will include clinical observation and monitoring of hematological and chemical parameters. Reactogenicity will be closely monitored for 7 days after injection and safety evaluated by clinical visits for 40 weeks following the vaccine administration and through an influenza season. See Section 4.4 and APPENDIX I: SCHEDULE OF EVALUATIONS for details and specified time points. The following endpoints will be assessed for all study groups:

- Occurrence of solicited local reactogenicity symptoms for 7 days after injection
- Occurrence of solicited systemic reactogenicity symptoms for 7 days after injection
- Occurrence of AEs of all severities through the 4-week post-injection visit
- Occurrence of AEs of change from baseline in safety laboratory measures
- Occurrence of SAEs or new chronic medical conditions that require ongoing medical management at any time through the study.

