## Laboratory Criteria within 56 days before enrollment:

- 9. White blood cells (WBC) and differential within institutional normal range or accompanied by the site Principal Investigator (PI) or designee approval
- 10. Total lymphocyte count  $\geq 800$  cells/ $\mu$ L
- 11. Platelets = 125,000 500,000 cells/µL
- 12. Hemoglobin within institutional normal range or accompanied by the PI or designee approval
- 13. Alanine aminotransferase (ALT)  $\leq$  1.25 x institutional upper limit of normal (ULN)
- 14. Aspartate aminotransferase (AST)  $\leq$  1.25 x institutional ULN
- 15. Alkaline phosphatase (ALP) <1.1 x institutional ULN
- 16. Total bilirubin within institutional normal range or accompanied by the PI or designee approval.
- 17. Serum creatinine  $\leq 1.1$  x institutional ULN
- 18. Negative for HIV infection by an FDA-approved method of detection

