## 5. SAFETY AND ADVERSE EVENT REPORTING

## 5.1. Adverse Events

Adverse Event (AE) - Any untoward medical occurrence in a human subject, including any abnormal sign (for example, abnormal physical exam or laboratory finding), symptom, or disease, temporally associated with the subject's participation in research, whether or not considered related to the subject's participation in the research. In the context of FDA-required reporting, an AE means any untoward medical occurrence associated with the use of a drug in humans, whether or not considered drug related. All AEs, including laboratory abnormalities, will be followed to resolution or stabilization.

Each AE will be graded according to the Toxicity Grading Scale for Healthy Adult and Adolescent Volunteers Enrolled in Preventive Vaccine Clinical Trials, Food and Drug Administration Guidance – September 2007 (APPENDIX II: ASSESSMENT OF RELATIONSHIP TO VACCINE AND GRADING SEVERITY OF ADVERSE EVENTS). The following guidelines will be used to determine whether or not an AE is recorded in the study database:

- 1. Solicited AEs (i.e., reactogenicity parameters as defined in Section 4.4.10) will be recorded without attribution assessments by the subject on paper or an electronic diary card for 7 days after injection. If the paper diary card is completed by subject, data will be transcribed by a clinician into the study database. Clinicians will follow and collect resolution information for any reactogenicity symptoms that are not resolved within 7 days.
- 2. All unsolicited AEs will be recorded with attribution assessments in the study database from receipt of the study injection through completion of the 4-week post-product administration visit. After that through the last study visit, only SAEs (Section 5.2), new chronic medical conditions, new diagnosed or potential autoimmune and auto-inflammatory diseases, and influenza or influenza-like illness (ILI) will be recorded.
- 3. Study clinicians will evaluate for cervical and axillary lymphadenopathy at every study visit through 14 days after vaccination, and if present, will assess for generalized lymphadenopathy. Lymphadenopathy will be reported as an unsolicited AE and followed to resolution through the end of the study.
- 4. Cases of influenza or influenza-like illness (ILI) will be evaluated as follows:

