#### 6.4.3.2 Adverse Events

AEs are coded into Medical Dictionary for Regulatory Activities (MedDRA) preferred terms. The number and percentages of participants experiencing each specific AE will be tabulated by severity and relationship to treatment. For the calculations in these tables, each participant's AE will be counted once under the maximum severity or strongest recorded causal relationship to treatment.

A complete listing of AEs for each participant will provide details including severity, relationship to treatment, onset, duration and outcome.

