#### 6.4.3.3 Local Laboratory Values

Boxplots, violin plots, or beeswarm plots of local laboratory values will be generated for baseline values and for values measured during the course of the study. Each plot will show the 1st quartile, the median, and the 3rd quartile. Outliers, or values outside the boxplot, will also be plotted. If appropriate, horizontal lines representing boundaries for abnormal values will be plotted.

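### The primary laboratory endpoint has no time window, no planned summary pairs a subject's values with Day 0, and Week 40 CBC and liver abnormalities outside the restricted AE categories appear only in plots

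*Combined protocol and SAP*

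**What the plan says.** **Endpoints (Section 6.3.1).** Two of the five primary safety endpoints concern us. One is "Occurrence of AEs of all severities through the 4-week post-injection visit", which carries its own window. The other is "Occurrence of AEs of change from baseline in safety laboratory measures", which has no window, no threshold for change and no summary measure. The section's introduction says safety is followed by clinic visits for 40 weeks.

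**AE definition and recording (Section 5.1).** Abnormal laboratory findings count as AEs. Unsolicited AEs are all recorded "from receipt of the study injection through completion of the 4-week post-product administration visit". From then to the last visit, recording is limited to SAEs, new chronic conditions, autoimmune or auto-inflammatory disease, and influenza or ILI.

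**AE analysis (Section 6.4.3.2).** "The number and percentages of participants experiencing each specific AE will be tabulated by severity and relationship to treatment". A listing for each participant accompanies the table.

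**Laboratory analysis (Section 6.4.3.3).** Box, violin or beeswarm plots of "local laboratory values will be generated for baseline values and for values measured during the course of the study". Quartiles and outliers are shown, and lines marking abnormal limits may be added. No table or paired summary is mentioned. Section 6.4.2 summarizes laboratory values descriptively at baseline only.

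**Baseline (Section 4.4.6 and the footnotes to Appendix I).** Day 0 evaluations before injection are the reference for later safety assessment.

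**The concern.** An endpoint worded as change from baseline leads the reader to expect each subject's later values to be compared with that subject's Day 0 value. The one section devoted to laboratory data plans plots of marginal distributions, which do not show who moved. If one subject rises and another falls by a similar amount, the picture can look the same as if nobody changed.

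The endpoint's scope is also unclear. If it means laboratory AEs through Week 4, it repeats part of the AE endpoint listed beside it. If it means more, for instance worsening up to Week 40, no table in Section 6.4 reports it. Two analysts could follow the plan faithfully and report different things under a primary endpoint.

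At stake is the readability of the laboratory safety result in groups of 5 to 15, where each subject counts. In Group 5, the adjuvanted group, one subject is 1/13 = 7.7 percentage points.

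**Working it through.** The plan gives no figure for this endpoint to reproduce. The check traces the endpoint through recording, grading and analysis, and counts scheduled draws.

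**1. Draws inside and outside full AE recording (Appendix I).**
- CBC and liver panel: Day 0, then Weeks 2, 4 and 40, so three post-dose draws.
- Creatinine: Day 0 and Week 2, so one post-dose draw.
- Subjects enrolled (Table 1): 5 + 15 + 15 + 13 + 13 = 61.
- Planned post-dose CBC/liver draws: 61 × 3 = 183, assuming every subject attends every visit.
- Draws at Week 40, after full AE recording has ended: 61 × 1 = 61, and 61/183 = 33%.

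A Week 40 CBC or liver abnormality enters an AE table only if it falls in a category still recorded after Week 4. Otherwise it appears only in the Section 6.4.3.3 plots. Creatinine has no Week 40 draw and is unaffected by this gap.

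**2. What a grade says about change (Appendix II).** Hemoglobin is the only analyte graded by decrease from baseline, from Grade 2 upward (1.6 gm/dL or more). The others use absolute cut-offs or multiples of ULN, and a value inside the institutional normal range is neither graded nor recorded as an AE. Two hypothetical cases: creatinine going from 0.7 to 1.4 mg/dL stays below Grade 1, which starts at 1.5. Eosinophils going from 100 to 600 per mm³ stay below Grade 1, which starts at 650.

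**3. Eligibility limits against Grade 1 (Section 4.2.1 and Appendix II).**

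| Analyte | Admitted at entry | Grade 1 | Overlap |
|---|---|---|---|
| ALT, AST | up to 1.25 x ULN | 1.1–2.5 x ULN | 1.1–1.25 x ULN |
| Lymphocytes | 800 or more | 750–1,000 | 800–1,000 |
| Platelets | 125,000–500,000 | 125,000–140,000 | 125,000–140,000 |

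The ALT/AST overlap lies above ULN, so the normal-range exemption does not remove it. The other two overlaps count only where the value is below the institutional range, which the documents do not give. Hence a post-dose Grade 1 does not by itself show worsening, and the plan has no table that would show the Day 0 grade next to it.

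**4. What the plots can show.** With 13 values and the upper quartile taken at position 1 + 0.75 × 12 = 10, the three highest values can rise by any amount without moving the median or quartiles. Extreme values would still be drawn as outliers, and a beeswarm plot draws every point. What none of these plots is specified to do is link a point to the same subject's Day 0 value.

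**The case against.** The strongest reply is that the endpoint concerns the occurrence of AEs, not change as a continuous measure, and that Section 6.4.3.2 delivers this. Laboratory findings are AEs, are graded under Appendix II, and are tabulated by severity and relationship and listed with onset, duration and outcome. This stands for events recorded through Week 4. It follows that several stronger readings are not supported:

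- **That plots are the only laboratory analysis.** The AE tables and listings also carry laboratory events.
- **That AE recording stops at Week 4.** It is restricted to named categories, and Section 5.1 has AEs, laboratory abnormalities included, followed to resolution or stabilization.
- **That Week 40 results go unreported.** They are plotted. What is missing is a table.
- **That Grade 1 values present at entry will be counted as vaccine effects.** Day 0 is the stated reference for AEs, and events are recorded only from injection onward with an attribution. What remains is that no rule says how much worsening from an abnormal Day 0 value makes an AE, and no table displays it.
- **That an eosinophil signal would be missed.** Sections 1.6.1 and 8.5.3 describe the elevation seen with another Adjuplex vaccine as transient. CBC with differential is drawn at Weeks 2 and 4, within full AE recording, and eosinophils have their own grades. This example does not support the Week 40 gap.

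A further objection is timing. Final dosing was on April 20, 2023 (Section 1.5.1), so Day 280 fell around late January 2024, while Version 7.0 is dated February 11, 2025. Rewording a primary endpoint in an open-label trial after its last scheduled visit would be a post hoc change. That is a reason to add the tables as supportive and leave the primary AE analysis in place.

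**Conclusion.** The point holds in a limited form. The laboratory endpoint lacks a window and a definition of change. No planned summary pairs laboratory values with Day 0, the hemoglobin-decrease grades being the only built-in comparison with baseline. Week 40 CBC and liver abnormalities outside the categories still recorded after Week 4 reach no table.

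The size is one of three post-dose CBC/liver draws, or 61 of 183 (33%), assuming full attendance by 61 subjects. How many abnormalities this involves cannot be known from the documents. The plan does deliver occurrence of laboratory AEs through Week 4, so a reader should not infer that a primary endpoint goes unanalyzed. This is a reporting gap in a descriptive Phase I analysis, and it is cheap to close.

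**What to change.** 1. In Section 6.3.1, state the window of the laboratory endpoint and how it differs from the AE endpoint through Week 4.
2. In Section 6.4.3.3, add for each analyte and by group:
   - a shift table of Day 0 grade against worst post-dose grade over the scheduled draws (Weeks 2, 4 and 40 for CBC and liver tests, Week 2 only for creatinine), with every value graded under Appendix II whether or not it was entered as an AE;
   - within-subject change from Day 0 at each visit, which also shows movement below the Grade 1 limits.
3. Keep the AE tables, the listing and the plots as they are.
4. If the tables are added after the data were collected, label them as supportive and say so.

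The cost is SAP wording and a few extra tables from samples already in the schedule. No visit, sample or clinical procedure changes.
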